14.3 Appendix 3: Assessment Windows

14.3.1 Definitions of Assessment Windows for Analyses

Not applicable.

2017N322544_01 **CONFIDENTIAL**

14.4 Appendix 4: Study Phases and Treatment Emergent Adverse Events

14.4.1 Study Phases

Assessments and events will be classified according to the time of occurrence relative to study treatment.

Treatment Phase	Definition
Pre-Treatment	Date/Time < Study Treatment Start Date/Time
On- Treatment	Study Treatment Start Date/Time ≤ Date/Time ≤ Study Treatment Stop Date/Time
Post- Treatment	Date/Time > Study Treatment Stop Date/Time

14.4.4.1 Study Phases for Concomitant Medication

Study Phase	Definition
Prior	If medication end date is not missing and is before 28 days prior to screening visit
Concomitant	Any medication that is not a prior

NOTES:

 Please refer to Appendix 7: Reporting Standards for Missing Data for handling of missing and partial dates for concomitant medication. Use the rules in this table if concomitant medication date is completely missing.

14.4.2 Treatment Emergent Flag for Adverse Events

Flag	Definition
Treatment Emergent	If AE onset date is on or after treatment start date & on or before treatment stop date. (plus washout or protocol-specified time limit (e.g. half-life of drug, certain number of days, etc.).
	Study Treatment Start Date/Time ≤ AE Start Date/Time.
	 For studies with greater than one treatment period (e.g., crossover study), if AE onset is during one period and worsens during a later period it would be counted in both periods. For the initial period the logic would be as above. For the later period the logic would use the treatment dates associated with the later period:
	 Treatment Period Start Date ≤ AE Worsening Date.

NOTES:

- If the study treatment stop date is missing, then the AE will be considered to be On-Treatment.
- Time of study treatment dosing and start/stop time of AEs should be considered, if collected.

14.4.3 Adverse Events Assignment to Treatment Period for Part 1

Adverse events (AEs) will be assigned to a treatment period and corresponding treatment received in that treatment period after the imputations defined in RAP section 14.7.3 have been performed.

35

- Treatment Period 1: all AEs with start date/time at the time of or after IMP administration in Treatment Period 1 and before IMP administration in Treatment Period 2
- Treatment Period 2: all AEs with start date/time at the time of or after IMP administration in Treatment Period 2 and before IMP administration in Treatment Period 3
- Treatment Period 3: all AEs with start date/time at the time of or after IMP administration in Treatment Period 3

Thus, AEs occurring during the 1st washout will be assigned to the treatment received in Treatment Period 1, AEs occurring during the 2th washout will be assigned to the treatment received in Treatment Period 2 and AEs occurring during follow-up will be assigned to the treatment received in Treatment Period 3.

14.4.4 Concomitant Medication Assignment to Treatment Period for Part 1

Concomitant medications (CMs) will be assigned to a treatment period and corresponding treatment received in that treatment period after the imputations defined in RAP section 14.7.3 have been performed.

- Treatment Period 1: all CMs with start date/time at the time of or after IMP administration in Treatment Period 1 and before IMP administration in Treatment Period 2
- Treatment Period 2: all CMs with start date/time at the time of or after IMP administration in Treatment Period 2 and before IMP administration in Treatment Period 3
- Treatment Period 3: all CMs with start date/time at the time of or after IMP administration in Treatment Period 3

Thus, CMs occurring during the 1st washout will be assigned to the treatment received in Treatment Period 1, CMs occurring during the 2th washout will be assigned to the treatment received in Treatment Period 2 and CMs occurring during follow-up will be assigned to the treatment received in Treatment Period 3.

36

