To assess the safety of GSK2838232 administered as non-boosted once-daily doses of a tablet formulation for 11 days	GSK2838232 safety parameters: adverse events; absolute values and changes over time of clinical laboratory evaluations (hematology, clinical chemistry, urinalysis), vital signs, and ECG parameters from pre-dose values
To assess the pharmacokinetics of GSK2838232 administered as non-boosted once-daily doses of a tablet formulation for 11 days	 Day 1 dose: AUC(0-τ), Cmax, Cτ, tmax, tlag Day 11 dose: AUC(0-τ), AUC(0-∞), Cmax, Cτ, tmax, t½, tlast
Secondary	1
To assess time to steady-state of GSK2838232 when administered as non-boosted once-daily doses of a tablet formulation for 11 days	Pre-dose concentrations on Days 2 to 11
To assess accumulation of GSK2838232 when administered as non-boosted once-daily doses of a tablet formulation for 11 days	• Accumulation ratios: Ro[AUC(0-τ)], R(Cmax), R(Cτ)

AUC(0- τ) = Area under the curve (Area under the plasma drug concentration-time curve from pre-dose to the end of the dosing interval at steady state); AUC(0-inf)= Area under the concentration-time curve from time zero (pre-dose) extrapolated to infinite time; Cmax= Maximum observed concentration; t1/2= Apparent terminal phase half-life; tmax= Time of occurrence of Cmax; tlag= Lag-time (time delay between drug administration and first observed concentration above LOQ in plasma); AUC (0-t) = Area under the concentration-time curve from zero up to a definite time t

Overall Design

Part 1:

Part 1 is a relative bioavailability study that will further subdivide into two parts (Part 1A and Part 1B) (Table 1). In Part 1A, the safety and pharmacokinetics (PK) of a novel tablet formulation of GSK2838232 will be evaluated in open label, randomized, cross-over fashion against the capsule formulation as reference. Each actual treatment dose will be separated by a minimum 10-day washout period. Part 1A will be studied in the fed state using a normal fat (i.e., approximately 30%) meal in all participants. In Part 1B, the tablet will be administered in the fasted state to understand the impact of food on relative bioavailability.

Table 1 Treatment Groups in Part 1

Sequence	N	Part 1A		Part 1B				
		Period 1	Period 2	Period 3				
1	6	A	В	С				
2	6	В	A					

- 1. All treatments in Part 1A to be administered with RTV in a fed state, following two RTV pre-doses.
- 2. There will be a washout of at least 10 days between each Period.

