- 3. Treatment A = $GSK2838232\ 200\ mg/r$ (as 4 x 50 mg) capsule formulation, fed, normal fat (i.e., approximately 30%) meal (reference).
- 4. Treatment $B = GSK2838232\ 200\ mg/r$ (as $2\ x\ 100\ mg$) tablet formulation, fed, normal fat (i.e., approximately 30%) meal.
- 5. Treatment C = GSK2838232 200 mg/r (as 2 x 100 mg) tablet, confirmed from Part 1A, fasted.

After completion of Part 1A, preliminary PK data will be analyzed, and a decision will be made based on safety, tolerability, relative bioavailability PK criteria, as well as feasibility considerations, as to whether the tablet formulation will be used to conduct Part 1B (fasted) and Part 2.

Part 2:

Part 2 will evaluate non-RTV boosted GSK2838232, given as single daily doses for 11 days in a separate cohort of participants (N=8; 6A/2P). The placebo tablet supplied will not be identical to GSK2838232 and as such will be administered by site staff via an opaque card/paper tube to facilitate the single blind (i.e., the Principal Investigator [PI] and the participants themselves will be blinded as to their treatment). The dose chosen for Part 2 will depend upon the preliminary results of the tablet in Part 1A but is likely to be, but will not exceed, 500 mg (i.e., 5 x 100 mg tablets) QD.

Number of Participants:

It is expected that a sufficient number of participants will be screened in order to enroll approximately 16 healthy participants to provide at least 12 evaluable participants through the three study periods for Part 1 and 10 healthy participants to provide at least 8 evaluable participants for the single study period of Part 2.

If participants prematurely discontinue the study, additional participants may be randomized and assigned to the same treatment sequence at the discretion of the Sponsor in consultation with the Investigator.

[figure not shown]
Treatment Groups and Duration:

GSK2838232 as tablets or capsules (at a 200 mg dose level) will be administered with 100 mg RTV, after two pre-doses of 100 mg RTV QD over 48 h. The use of RTV priming is an aspect of GSK2838232 clinical development (specifically relative bioavailability studies) so far and allows a more accurate assessment of what will ultimately happen in the repeat-dose clinical studies with GSK2838232 when administered with RTV. In Part 2 of the study however, GSK2838232 will be administered unboosted and no RTV will be co-administered.

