2. SCHEDULE OF ASSESSMENTS

Please see Table 2 and Table 3 below for the Schedule of assessments for study Parts 1 and 2 respectively.

Table 2 Schedule of Assessments for Part 1A and Part 1B: Single Dose RBA \pm Food

	Screening (within 30 days of	Periods 1 through 3													
Procedure	Day 1 - carried out over multiple days – except as noted in	Day -3	Day -2	Day -1	Day 1	Day 2	Day 3	Day 4	Day 5	Day 6	Day 7	7-14 days			
	footnotes)					24 h	48 h	72 h	96 h	120 h					
Admission to Unit	,	X2													
Outpatient Visit	Х											Х			
Informed Consent	Х														
Medical/medication/															
drug/alcohol history (Demographics)	X														
Full Physical Examination	Х														
Brief Physical Examination			Х				Х					Х			
Height, Weight, BMI	Х														
Inclusion/Exclusion	Х														
Vital signs ³	Х		Х	Χ	Χ	Χ	Х	Χ				Х			
12 Lead ECG ⁴	Х		Х	Χ	Χ	Χ	Х					Х			
Echocardiogram ⁵	Χ														
Drug/alcohol/cotinine screen	Χ	Х													
HbsAg, HCV, HIV tests	Χ														
Hem/Chem/Urine tests ⁶	Х		Х	Х		Х		Х				Х			
Serum FSH (as appropriate)	Х														
Troponin I ⁷	Х			Х	Χ	Χ		X							
24 h Holter Monitoring ⁸	Х														
Pregnancy test (women)	Χ	Χ										Χ			
Run-in Dosing with RTV			X	Χ											
Dosing with GSK2838232+RTV					X										
PK Sampling ⁹					X	Χ	X	Χ	Χ	X					
Adverse Event Review ¹⁰				X	Х	Χ	Х	Χ	Х	Х	Χ	Х			
Con Med Review			X	Χ	Χ	Χ	X	Χ	Χ	X	Χ	X			
Discharge from Unit ¹¹						X									
Out Patient Visit							X	Х	X	Χ	Χ				

BMI = Body Mass Index; ECG = Electrocardiogram; FSH = Follicle Stimulating; HbsAg = Hepatitis B surface Antigen; HCV = Hepatitis C Virus; HIV = Human Immunodeficiency Virus; Hem/Chem = Hematology/Clinical Chemistry; RTV = Ritonavir; PK = Pharmacokinetic(s); Con Med = Concomitant medications.

- 1. Follow-up Visit to take place after Treatment Period 2.
- 2. When participants stay in the unit across treatment periods, drug/alcohol/cotinine screen and pregnancy test (women) are not required on Day -3 for later periods.
- 3. On Day 1, Blood pressure (BP) and Heart rate (HR) will be collected at pre-dose (triplicate) and single assessments at 1, 2, 4, 6, 8, 12, 24, 48, and 72 h post-dose.
- 4. On Day 1, 12-lead ECG will be collected at pre-dose (triplicate), and single assessments at 1, 2, 4, 6, 8, 12, 24, 48 and 72 h post-dose.
- 5. Echocardiograms must be within 100 days of Day 1.
- 6. Samples for Chemistry and Hematology: Blood samples will be obtained after an 8-hour fast.

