3.3.1. Risk Assessment

Potential Risk of Clinical Summary of Data/Rationale for Risk Significance		Mitigation Strategy		
	Investigational Product (IP) GSK2838232			
Cardiovascular	Pre-clinical studies have shown the following findings: elevated heart rates, an isolated episode of non-sustained ventricular tachycardia and minimal to mild, sporadic troponin I elevations in dogs. A subsequent investigative cardiovascular study in telemetered dogs treated for four weeks did not replicate these effects. Isolated microscopic cardiovascular changes were noted (focal extramural arteritis and localized epicardial inflammation), however these changes were considered of uncertain relationship to GSK2838232 because similar findings occur at low incidence in normal beagles and there were no GSK2838232-related functional changes by telemetry and echocardiography, or changes in cTpnI and NTproBNP. In addition, there was no correlation between histologic changes and plasma exposure or heart tissue concentrations of GSK2838232. Toxicology studies in rat and dog (3, 6 and 9 months) did not demonstrate any evidence of cardiovascular injury or impact on cardiovascular function. In the four GSK2838232 studies conducted so far, there was no pattern of cardiovascular changes of clinical significance related to GSK2838232 and no	Participants will be clinically monitored for any signs of myocardial injury (chest pain, shortness of breath, pain with inspiration), elevated heart rate or arrhythmias. Samples for the assessment of troponin will be taken. Baseline ECG and Holter (to use for screening and for later comparisons if needed) Exposures of GSK2838232 will be closely monitored in the clinical study so as to not exceed PK stopping criteria.		

Potential Risk of Clinical Significance	Summary of Data/Rationale for Risk	Mitigation Strategy	
	clinically significant abnormality in electrocardiogram (ECG) values other than the two serious adverse events (SAEs) documented and discussed.		
	Review of published bevirimat preclinical and clinical safety data indicates no significant toxicities or adverse events (AEs) of interest, other than a 30% incidence of gastrointestinal symptoms (including diarrhea). There were no significant cardiovascular AEs reported in published clinical studies.		

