- 4. Treatment B = GSK2838232 200 mg/r (as $2 \times 100 \text{ mg}$) tablet formulation, fed, normal fat (i.e., approximately 30%) meal.
- 5. Treatment C = GSK2838232 200 mg/r (as 2 x 100 mg) tablet, confirmed from Part 1A, fasted.

After completion of Part 1A, preliminary PK data will be analyzed, and a decision will be made based on tolerability, relative bioavailability PK criteria, as well as feasibility considerations, as to whether the tablet formulation will be used to conduct Part 1B (fasted) and Part 2.

Part 2:

Figure 2 Single Daily Dose Study Design Schematic

- Part 2 will evaluate non-RTV boosted GSK2838232, given as single daily doses for 11 days in a separate cohort of participants (N=8; 6A/2P).
- The placebo tablet supplied will not be identical to GSK2838232 and as such will be administered by site staff via an opaque card/paper tube to facilitate the single blind (i.e., the Principal Investigator [PI] and the participants themselves will be blinded as to their treatment).
- The dose chosen for Part 2 will depend upon the preliminary results of the tablet in Part 1A but is likely to be, but will not exceed, 500 mg (i.e., 5 x 100 mg tablets) QD.
- Participants will have a screening visit within 30 days prior to first dose, and a follow-up visit 7 to 14 days after the last dose. The maximum duration of study participation will be approximately 8 to 9 weeks.

Study Population:

The study population will consist of healthy male or female participants (women of child bearing potential [WOCBP] are permitted as long as the criteria for contraception are adhered to), as per inclusion/exclusion criteria (Section 6).

Note: Participants in both Part 1 and Part 2 will have a 24-h Holter screen as part of baseline evaluation. Holter monitoring may apply during the study period if needed.

Study Plan:

Because of the requirement to begin RTV pre-dosing 48 hours before each treatment dose in Parts 1A and 1B, participants will be admitted to the Clinical Unit three nights before each of the treatment periods and remain in the Unit until the last (120 h) PK time-point of each treatment period is collected. There is no such early admission requirement for Part 2 (non-boosted GSK2838232).

205820

If participants prematurely discontinue the study, additional participants may be randomized and assigned to the same treatment sequence at the discretion of the Sponsor in consultation with the Investigator.

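### The Part 1 adverse event windows hang on an undefined term and overlook the ritonavir run-in, so on the likelier reading run-in events in Periods 2 and 3 are tabulated under the previous period's treatment

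*SAP*

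**What the plan says.** SAP 14.4.3 (Appendix 4) gives the rule for Part 1. Period 1 takes "all AEs with start date/time at the time of or after IMP administration in Treatment Period 1 and before IMP administration" in Period 2. Period 2 has the same form, and Period 3 runs from its own IMP administration with no closing point. The section then spells out one consequence: "AEs occurring during the 1st washout will be assigned to the treatment received in Treatment Period 1". Washouts and follow-up are named; the ritonavir run-in is not.

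The run-in is part of every Part 1 period. The Protocol Synopsis has GSK2838232 given with ritonavir "after two pre-doses of 100 mg RTV QD over 48 h". Protocol 5.1 explains the early admission in these terms: "Because of the requirement to begin RTV pre-dosing 48 hours before each treatment dose in Parts 1A and 1B". Table 2 of the protocol, repeated in SAP 14.2.1, marks "Run-in Dosing with RTV" on Days -2 and -1 of Periods 1 through 3, and marks "Adverse Event Review" from Day -1, so events during the run-in will be asked about.

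IMP has no definition in either document; the SAP abbreviation list has only IP. SAP 5.1 gives three Part 1 columns: capsule fed, tablet fed and tablet fasted. The SAP addendum does not list 14.4.3 among its changes.

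**The concern.** Each window closes at the next IMP administration. If that means the next GSK2838232 dose, the last 48 hours before it, when the participant is taking ritonavir for the coming period, still belong to the treatment given at least 10 days earlier. Protocol 3.3.3 expects ritonavir-related events in Part 1, and Protocol 10.4.1 tabulates events by treatment group. A ritonavir event would then appear under a formulation that did not prompt that ritonavir dose. Two programmers who read IMP differently could also produce different Part 1 tables from the same data.

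At stake is the accuracy of the by-treatment tables that report the Part 1 secondary safety objective.

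**Working it through.** The plan states no figure on this point, so the check applies the rule to the schedule.

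**Which reading of IMP is likelier**

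| Source | Points to |
|---|---|
| Protocol 3.3.1: the risk table labels the drug "Investigational Product (IP) GSK2838232" | GSK2838232 |
| Protocol 7.1, Table 5: the title separates investigational product from other study treatment | GSK2838232, though it does not say which drug is which |
| SAP 5.2: Day 1 pre-dose values may serve as baseline in each Part 1 period, although two ritonavir doses have been given by then | GSK2838232 |
| SAP 14.6.2: planned treatment duration in Part 1 is 1 day | GSK2838232 |
| Protocol Table 1, note 1: "All treatments in Part 1A to be administered with RTV in a fed state, following two RTV pre-doses" | run-in as part of the treatment |

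The balance favours GSK2838232 but does not exclude the other reading.

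**Where a run-in event goes**

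Put the GSK2838232 doses at 0, g and 2g days, with ritonavir starting 48 h before each. Events starting on Day -2, on Day -1 or pre-dose on Day 1 all get the same result, and g = 10, 12 and 14 days give the same assignments (10 is the documented minimum; 12 and 14 are assumed).

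| Run-in of | IMP = GSK2838232 | IMP includes ritonavir |
|---|---|---|
| Period 1 | no period | Period 1 |
| Period 2 | Period 1 | Period 2 |
| Period 3 | Period 2 | Period 3 |

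**By treatment, for 12 completers (6 ABC, 6 BAC), IMP = GSK2838232**

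- Total run-ins: 12 × 3 = 36.
- ABC: the Period 2 run-in goes to A and the Period 3 run-in to B, so A 6, B 6.
- BAC: the Period 2 run-in goes to B and the Period 3 run-in to A, so B 6, A 6.
- Sum: capsule fed (A) 12, tablet fed (B) 12, tablet fasted (C) 0, no period 12.

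A completer of either sequence adds one run-in to A and one to B, so the A and B counts are equal whatever the split between sequences. If IMP includes ritonavir, the counts are A 12, B 12, C 12, none unassigned, each in its own period.

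**Share of the window**

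Share = 48 h / (24 h × dose spacing in days), for the Period 1 and Period 2 windows. Period 3 contains no later run-in.

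- Spacing 10 days (washout counted dose to dose): 48/240 = 20%.
- Spacing 12 days (assumed): 48/288 = 16.7%.
- Spacing 14 days (assumed): 48/336 = 14.3%.
- Spacing about 19 days (washout counted between periods, with Table 2 periods running from Day -3 to Day 7): 6 days from dose to Day 7, plus 10, plus 3 days from Day -3 to Day 1 = 19; 48/456 = 10.5%.

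The protocol words the washout both ways, so both ends belong in the range. The 19-day spacing fits a 10-week participation if screening takes no more than 70 − 2 × 19 − 7 = 25 days, which the 30-day limit allows.

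**One event**

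Moving one participant's event changes a column by at most 1/12 = 8.3 percentage points (1/16 = 6.3 if all 16 enrolled count). It changes nothing if that participant already had the same term under that treatment.

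**The case against.** The strongest reply is that IMP may include ritonavir. Run-in events then fall in their own period, which is a defensible convention because the treatments are defined as following the pre-doses. That reading is open, but the SAP does not state it and four places lean the other way.

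Three stronger inferences are tempting, and the documents do not support them.

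- *Period 1 run-in events are wrongly lost.* They match no bullet if IMP is GSK2838232. This conflicts with the treatment-emergent flag in SAP 14.4.2 only if study treatment there includes ritonavir, as Protocol 7 defines it. If the SAP means GSK2838232 in both places, these events are pre-treatment under 14.4.1, and having no treatment column is consistent.
- *The tablet-versus-capsule safety comparison is distorted.* It is not: both fed columns carry 12 misplaced run-ins. Only the fasted column differs. It is always Period 3 and already takes follow-up time in place of a washout.
- *Reassignment changes which events pass the 5% cutoff of Table 3.3.* That table is by overall frequency, which a move between columns leaves unchanged, and one participant in 12 or 16 already exceeds 5%.

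There are also safeguards. All adverse events are listed, the investigator judges causality for each, and an event that worsens in a later period is counted there as well under 14.4.2. These limit the harm but do not correct the by-treatment tables.

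**Conclusion.** The point holds as a minor one. It is more than a missing definition: on the likelier reading, the rule as written gives Period 2 and Period 3 run-in events to the wrong period's treatment. The size is 12 run-ins charged to capsule fed, 12 to tablet fed and 0 to tablet fasted, with about 10.5% to 20% of each Period 1 and Period 2 window belonging to another period's run-in.

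This rests on IMP meaning GSK2838232, on 12 completers, and on dose spacing between 10 and about 19 days; a longer spacing gives a smaller share. How many events would start in a run-in is not known. A reader might infer that the Part 1 safety conclusions or the bioavailability results are compromised. The documents do not support that: no adverse event comparison is tested, the tables are descriptive and secondary, and the pharmacokinetic analyses do not use these windows.

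**What to change.** In SAP 14.4.3, define IMP and state that each Part 1 period's adverse event window opens at that period's first ritonavir run-in dose and closes just before the next period's first ritonavir dose, or at follow-up for Period 3. Run-in events are then tabulated in their own period. Align the start of study treatment in 14.4.1 and 14.4.2, and the period start used in the worsening rule, with the same anchor. SAP 14.4.4 uses the same IMP wording for concomitant medications, so it should be read against the same definition.

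A separate ritonavir run-in column, with a matching label in SAP 5.1, is an option and not a necessity: no objective asks for a ritonavir-only event rate.

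The cost is a few sentences and a derivation from dose dates and times, which Protocol 7.6 already requires at source. If the tables have already been produced, the study report should state which convention was programmed. Dosing, data collection and the pharmacokinetic analysis do not change.
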